#### Investigational Medicinal Product (IMP)

The study involves 2 drug compounds - sofosbuvir 400mg and velpatasvir 100mg, available as a fixed-dose combination single tablet, marketed under the brand name 'Epclusa'. The IMP is taken orally once per day for 12 weeks, in addition to standard 12 weeks of sofosbuvir/velpatasvir (total 24 weeks treatment).

The recommended treatment for all genotypes of HCV according to EU license is as follows:

- patients without cirrhosis and with compensated cirrhosis Epclusa (sofosbuvir/velpatasvir 400/100mg) for 12 weeks; addition of ribavirin may be considered for genotype 3 infected patients with compensated cirrhosis
- patients with decompensated cirrhosis Epclusa + ribavirin for 12 weeks

Patients co-infected with human immunodeficiency virus (HIV) and patients with recurrent HCV post-liver transplant follow the same recommendation.

Mechanism of action: Velpatasvir is an inhibitor of the HCV non-structural (NS) 5A protein, which exerts activity across all genotypes (1-6) of HCV. Sofosbuvir is an inhibitor of the HCV NS5B RNA polymerase. Both proteins are essential for HCV replication.

Safety: The safety profile of Epclusa is based on pooled data in 1035 patients from Phase 3 clinical studies of patients with or without compensated cirrhosis, who received 12 weeks of sofosbuvir/velpatasvir. The most frequently reported adverse reactions were headache (29%), fatigue (25%) and nausea (14%). These and other adverse events were reported at a similar frequency in placebo treated patients. The proportion of patients who discontinued treatment due to adverse events was 0.2% and the proportion of patients who experienced severe adverse events was 3.2%. [8]

The safety profile of sofosbuvir/velpatasvir (with and without ribavirin) in Child Pugh B decompensated cirrhosis has been evaluated in one open-label study of 267 patients, including 90 patients who received 24 weeks of sofosbuvir/velpatasvir (without ribavirin). Observed adverse events were consistent with the expected clinical sequelae of decompensated liver disease, or the known toxicity profile of ribavirin. Anaemia occurred in 3-4% in patients using 12-24 weeks of sofosbuvir/velpatasvir, which increased significantly to 31% with addition of ribavirin [16].

For further information on the clinical pharmacology, virology, safety and efficacy of sofosbuvir + velpatasvir, please refer to the Summary of Product Characteristics.

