As outlined above there is no clear evidence that extended duration of therapy with sofosbuvir/velpatasvir increases the response to therapy and therefore it is unclear whether or not the increased side effects associated with extended duration therapy are justified. In a direct comparison between 12 and 24 weeks of therapy in patients with advanced cirrhosis, there was no significant increase in adverse events observed in the extended duration [16]. Large cohort studies in patients with advanced liver disease have highlighted the potential risks of antiviral therapy with reports of rare but significant side effects including drug induced liver damage [24] and lactic acidosis [25]. Clearly prolonged exposure to unnecessary therapy should be avoided.

Response-guided therapy in which the duration of anti-viral therapy is modified depending upon early virological response was widely used in patients receiving interferon based treatments for chronic HCV infection [26]. This approach is therefore feasible and accepted by patients. However this approach has not yet been evaluated for DAA treatments aside from retrospective studies. Response guided therapy allows optimisation of scarce NHS resources providing significant population benefits and reduces drug exposure in individual patients, thereby reducing side effects. This trial therefore has the potential for both societal and individual patient benefits. The value of response-guided therapy for high cost DAA treatments and need for prospective trials to evaluate its utility has been recently widely discussed and called upon [27, 28].

There is no established second line therapy for patients who fail to respond after treatment with current DAA treatments, and retreatment is not offered on the NHS treatment programme. However clinical trials of new 'triple therapy' regimens involving sofosbuvir, novel NS5A inhibitors and novel protease inhibitors are on-going and it is probable that such treatments will be available in the near future.

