#### 13.5 Patient Allocation

#### 13.5.1 Randomisation Method

Participants who fulfill inclusion/ exclusion criteria will be randomised. This takes place anytime after enrolment between treatment week 8 to 12. Sites must ensure sufficient time to randomise participants and dispense additional IMP for those in the arm B (24 weeks) such that there will not be more than 24 hours before commencing week 13 treatment.

Participants will be allocated into treatment arms A and B in a 1:1 ratio, by block randomisation, and stratified by whether they have compensated cirrhosis or decompensated cirrhosis at baseline. Participants with previous history of decompensation will be considered as having decompensated cirrhosis for the purpose of stratification. This is in order to generate equal numbers within each arm, with balanced severity of liver disease distributed. Clinical trial data suggests that severity of liver disease and presence of decompensated cirrhosis are one of the most important factors determining treatment outcome [8].

There may be other patient factors which influence treatment success, but further stratification for a study of 60 participants would not be appropriate. Block randomisation will enable interim analysis to be performed with balanced groups.

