# 19.0 Statistical and Data Analysis

#### 19.1 Sample size calculation

The planned sample size is 60 participants - with 30 participants in each of two treatment arms. This is based on the assumption of a 30% difference in the primary outcome measure (proportion of patients who achieve SVR12) between the two treatment arms, where SVR in the 12 week treatment arm is 65%, and 95% in the 24 week treatment arm. All outcomes are measured on an intention to treat basis.

Estimates of SVR rates for patients with slow treatment response (week 2 HCV detectable) is derived from post-hoc analyses of cohort studies or clinical trials. For genotype 3 patients with decompensated cirrhosis treated with sofosbuvir and NS5A inhibitor (daclatasvir or ledipasvir) with or without ribavirin, SVR was 65% for patients viraemic at week 2 [14]. There is no data available for this subgroup treated with sofosbuvir/velpatasvir. For all genotype 3 patients with decompensated cirrhosis, SVR was 50% after 12 weeks of sofosbuvir/velpatasvir [16], and 91% for patients with compensated cirrhosis [15]. Another study showed that a combination of 3 negative factors in genotype 3 patients dropped SVR after 12 weeks of sofosbuvir/velpatasvir to 85%, from 95% if only 2 negative factors were present [18].

Given the trial cohort will contain compensated and decompensated patients, the SVR after 12 weeks is estimated at 65%. The study assumes an SVR of 95% with the extended arm, in order for the margin of improvement to be clinically and statistically significant, as well as cost-effective to justify the increased drug costs. This is a realistic assumption given 12 weeks of sofosbuvir/velpatasvir in genotype 3 patients without negative factors (i.e. without cirrhosis) achieved SVR of 97% [15]. This study will demonstrate if treatment extension can overcome the impact of negative treatment factors on SVR.

To detect a true difference between the two treatment arms (if one exists) with 80% power and 95% confidence level, 24 participants are required as a minimum in each arm. The study will recruit 60 participants to allow for withdrawals or those lost to follow up.

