#### 19.2 Planned recruitment rate

The study plans to recruit 60 participants from 5 London sites in 9 months. Each site therefore has to recruit 12 patients, at a rate of less than 2 patients per month.

There are estimated 10,000 HCV infected individuals in England who have cirrhosis. Around 45% may be infected with genotype 3. The study target group is enriched within London where there is a high immigrant population (where genotype 3 HCV prodominates) and a concentration of patients with cirrhosis or advanced liver disease, currently over 30% of treated patients nationally have cirrhosis. At Royal London Hospital (one of the study sites), approximately 3 new patients with genotype 3

HCV are identified to start treatment each week. Amongst patients treated within the Expanded Access Programme, around 50% of patients did not achieve undetectable HCV after 2 weeks of treatment. In a phase 3 trial of 12 weeks of sofosbuvir/velpatasvir, which did not include the hardest to treat patients with decompensated cirrhosis, 38% did not achieve undetectable HCV at treatment week 2, and this is expected to be higher for a cohort including decompensated cirrhosis [20].

Sofosbuvir/velpatasvir is due to become routinely available as NHS treatment in the upcoming months. The number of prescriptions for high cost interferon-free therapies for genotype 3 patients is determined by the treatment centre's 'run rate'. Participating sites have indicated that the number of subjects required for recruitment is within their run rate allowance.

Given the entry criteria for the study match the NHS eligibility criteria for sofosbuvir/velpatasvir use, identification of suitable patients for recruitment, using the NHS treatment network, will be straightforward. Chosen study sites are all experienced HCV treatment and clinical trial centres, with a good track record of recruitment for regional and international studies.

Based on the low discontinuation rate on the Expanded Access Programme in England, where real world patients with advanced liver disease were treated [14], the study does not anticipate premature treatment or study withdrawal to be a major problem. The study will recruit patients who adhered to 90% of their treatment at screening, to eliminate the risk of early drop outs.

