# 19.6 Secondary outcome analysis

Secondary endpoints - safety analysis

- proportion of patients requiring study treatment discontinuation
- proportion of patients with serious adverse events (SAEs) during study period (ie treatment period + follow up)

Secondary endpoint - quality of life

• Short-Form Health Survey (SF36) scores at the end of treatment and 3 months post-treatment for both treatment arms. Score range from 0-100, with the highest score representing best quality of life. For each treatment arm, group mean scores at both time points, as well as the change from end of treatment to post-treatment, will be analysed.

To evaluate the tolerability of extended treatment, it is important that any randomised participant who takes at least one dose of the extended phase treatment is included in the analysis.

Comparison of proportions will be analysed by Chi-square test. Comparison of means of continuous variables will be analysed by T-test.

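### Discontinuation and SAE proportions are compared only by chi-square at about 30 per arm; a risk difference with a score-type interval should be the main comparison, because a non-significant p-value would say little about tolerability

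*Protocol*

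**What the plan says.** Protocol section 19.6 lists two safety endpoints: the proportion needing study treatment discontinuation and the proportion with an SAE over treatment and follow-up. It then gives the method for all secondary endpoints: "Comparison of proportions will be analysed by Chi-square test. Comparison of means of continuous variables will be analysed by T-test". No interval for a difference in proportions and no provision for sparse counts appears there. Section 19.3 says that the pre-specified analyses are the ones set out in the sections that follow it, so the test is fixed in the protocol itself.

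On size, section 19.1 states: "The planned sample size is 60 participants - with 30 participants in each of two treatment arms". Section 13.5.1 adds: "Participants will be allocated into treatment arms A and B in a 1:1 ratio".

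On event rates, the account of the investigational product in section 9.1 says: "The proportion of patients who discontinued treatment due to adverse events was 0.2" per cent, and gives 3.2% for severe adverse events. Both come from pooled 12-week data in patients without cirrhosis or with compensated cirrhosis. Section 19.2 adds that "the study does not anticipate premature treatment or study withdrawal to be a major problem".

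The objective in section 11.2 is to assess safety and tolerability. It carries no safety hypothesis, margin or power target.

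**The concern.** If events are rare, a chi-square test on 30 against 30 either cannot be computed (no events in either arm) or returns a p-value that is nearly always above 0.05, even when the true increase is large enough to matter clinically. The p-value does not show how large an increase has been ruled out.

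That matters because section 9.1 speculates that the gain in response will justify any added side effects of the longer course, and section 19.6 itself stresses evaluating the tolerability of the extension. A bare p>0.05 is easily taken as reassurance. In its account of previous evidence, section 9.2 already reports that "there was no significant increase in adverse events observed in the extended duration".

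**Working it through.** **Inputs.** 30 per arm, 1:1 (sections 19.1 and 13.5.1). Rates of 0.2% and 3.2% (section 9.1), used only as proxies. Higher rates of 5%, 10%, 15% and 20% are assumptions, because the protocol gives no SAE rate. The two-sided 5% level is also an assumption for the safety tests.

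**The plan's own sample size.** Section 19.1 assumes a setting "where SVR in the 12 week treatment arm is 65%, and 95% in the 24 week treatment arm", and concludes that "with 80% power and 95% confidence level, 24 participants are required as a minimum in each arm". With unpooled variances:

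n = (1.960 + 0.842)² × [0.65×0.35 + 0.95×0.05] / 0.30² = 7.849 × 0.275 / 0.09 = 23.98, so 24.

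The figure reproduces. It concerns SVR12 only; the protocol makes no size or power statement for the safety comparisons.

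**Chance that the statistic is undefined.** With the same rate p in both arms, P(no event in 60 patients) = (1 − p)^60.

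| Rate p | (1 − p)^60 |
|---|---|
| 0.2% | 0.998^60 = 88.7% |
| 1% | 0.99^60 = 54.7% |
| 2% | 0.98^60 = 29.8% |
| 3.2% | 0.968^60 = 14.2% |
| 10% | 0.90^60 = 0.2% |

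**Expected counts.** With equal arms the expected count in each event cell is half the total number of events, so it is below 5 whenever there are fewer than 10 events in 60. This happens in essentially 100% of trials at 0.2% or 3.2%, in 93% at 10% and in 21% at 20%.

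**Type I error and power of the uncorrected Pearson test**, by summing both binomials over all 31 × 31 tables:

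- Type I error is 1.1% at 3.2%. Its maximum over rates from 0.1% to 50% is about 5.5%, near 12%.
- Power is shown below, with Fisher's exact test for comparison.

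| 12 weeks vs 24 weeks | Pearson | Fisher |
|---|---|---|
| 3.2% vs 6.4% | 5.2% | 0.4% |
| 3.2% vs 9.6% | 14.7% | 2.6% |
| 5% vs 15% | 26.4% | 9.3% |
| 10% vs 20% | 19.4% | 9.6% |
| 15% vs 30% | 28.1% | 19.2% |
| 20% vs 40% | 39.2% | 29.8% |

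For scale, 80% power to detect 3.2% vs 6.4% would need about 700 per arm.

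**What an interval shows.** The Newcombe 95% interval for d = p24 − p12 combines the Wilson limits (l, u) of each arm:

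lower = d − √[(p24 − l24)² + (u12 − p12)²]; upper = d + √[(u24 − p24)² + (p12 − l12)²].

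- 0/30 vs 0/30: Wilson limits are 0 and 0.1135 in each arm, so the interval is −11.4 to +11.4 points. The chi-square does not exist.
- 3/30 (24 weeks) vs 1/30 (12 weeks): d = 0.0667; Wilson limits are 0.0346 to 0.2562 and 0.0059 to 0.1667. Lower = 0.0667 − √(0.0654² + 0.1333²) = −0.082. Upper = 0.0667 + √(0.1562² + 0.0274²) = +0.225. The interval is −8 to +23 points; the chi-square gives only p = 0.30.

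**The case against.** Much of the case on the other side stands.

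- **The rates are not rates for these endpoints.** The 3.2% is for severe events, whereas the endpoint is serious events, and section 17.2 warns against confusing the two. The 0.2% counts only stops for adverse events, whereas the endpoint is any discontinuation of study treatment. Both exclude decompensated patients, whom section 12.1 admits. A reader might infer that the test is often undefined for both endpoints. The documents support that only for discontinuation, and only if its rate is close to 0.2%.
- **The low power comes from 30 per arm.** Exact tests do worse, as the Fisher column shows. A reader might infer that the chi-square should give way to an exact test. The low power does not support this, and with type I error at most about 5.5% the chi-square is not materially anti-conservative.
- **The objective is only to assess.** A reader might infer that the plan cannot meet its tolerability objective. That goes too far: no safety hypothesis is stated, and per-arm proportions are already the endpoints.
- **Nothing in section 19.6 says that p>0.05 will be read as safe.** The remark in section 9.2 describes an earlier trial, and the same section calls it unclear whether added side effects are justified.
- **An interval could sit in a statistical analysis plan.** It could. But the protocol has already named a method, and it is the less informative one.

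One limit applies to the fix as well. Section 11.6 has Arm A in the study for up to 16 weeks and Arm B for up to 28, so a crude difference in SAE proportions partly reflects observation time, whichever method is used.

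**Conclusion.** The point holds in a limited form. For discontinuation and SAEs the protocol names only a chi-square test, and at 30 per arm its p-value will say little about tolerability. Its power for a doubling is about 5% from a 3.2% base, 19% from 10% and 39% from 20%. The statistic is undefined in about 89% of trials at a 0.2% rate and about 14% at 3.2%, with the problem disappearing at 10% or more. A non-significant result could coexist with intervals reaching +11 points (no events at all) or +23 points (3/30 vs 1/30).

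This rests on proxy and assumed rates, because the protocol states no SAE rate, and on full arms of 30. The weakness is an uninformative null result. It is not an inflated error rate, and a different significance test would not cure it.

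**What to change.** In section 19.6, for discontinuation and SAEs:

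1. Report the number and percentage in each arm.
2. Make the risk difference (24 minus 12 weeks) with a score-type 95% confidence interval the main comparison. Newcombe's interval is one suitable choice, and it is defined with zero events.
3. State that a non-significant p-value will not be read as evidence of equal tolerability.

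Any p-value is then secondary and the choice of test is optional, since exact tests have lower power here. When reporting the SAE difference, give the length of observation in each arm beside it.

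The cost is a few sentences and a few lines of code, with no added patients or data. The downside is that the intervals will be wide and the safety statement will look less reassuring.

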#### 19.7 Subgroup analyses

Subgroup analysis, with consideration to sample size, will be performed as appropriate. Important subgroups include gender, previous HCV treatment history, and whether compensated or decompensated cirrhosis (randomisation will be stratified by this baseline factor).

#### 19.8 Adjusted analysis

Adjusted analysis or other post-hoc analysis will be performed as appropriate.

#### 19.9 Interim analysis and criteria for the premature termination of the trial

An interim analysis of efficacy and safety will be considered through discussion with the Trial Steering Committee when about half the planned sample size is recruited to evaluate if there is an indication to discontinue the trial, alter the sample size, or replace participants who withdraw.

# 19.10 Subject population

All data will be reported on an intention to treat basis such that all randomised participants who received one dose of study drug will be included (entry criteria dictates all participants have adhered to 90% of treatment at the point of screening). Per protocol analysis will be analysed and reported as appropriate, for instance if there is an unexpectedly high treatment discontinuation or lost to follow up rate. For per protocol analysis, participants who adhered to 90% of their treatment according to randomisation will be included.

# 19.11 Procedure(s) to account for missing or spurious data

To reduce missing data on the primary outcome, SVR12 will be defined as HCV RNA <15iu/mL from 12 to 16 weeks after end of treatment. This widens the window when SVR12 can be reported. A negative HCV RNA at any point after 12 weeks post-treatment is clinically considered to be a sustained virological cure. Negative HCV RNA at less than 12 weeks post-treatment will be considered non-SVR12.

Non SVR12 will be differentiated by true viral relapse or missing data due to lost to follow up, to allow per-protocol analysis.

Given data is time point specific, data outside of the defined window cannot be carried forward to replace missing data.

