### 11.3 Endpoints

#### 11.3.1 Primary Endpoint

Proportion of patients with undetectable HCV RNA (below limit of quantification up to 15 iu/mL) in serum at 12 weeks (+ 4 weeks) after end of treatment (SVR12)

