# 13.11 End of trial (EOT)

The CI is delegated the responsibility of submitting the EOT notification to REC and MHRA once reviewed by sponsor. The EOT notification must be received by REC and MHRA within 90 days of the end of the trial.

If the study is ended prematurely, the Chief Investigator will notify the Sponsor, REC & MHRA including the reasons for the premature termination (within 15 days).

End of trial is defined as 3 months after the last randomised participant completes the study procedures.

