# 15.19 Assessment of compliance

Compliance will be monitored via pill counting and checking returned empty bottles during study visits. Missed pills will be documented in CRF. Investigators will reiterate dosing schedule and the importance of compliance for efficacy. Participants are considered lost to follow up if there is no end of study visit at post treatment week 12+4 weeks.

There is no provision for supplying additional IMPs which are lost or damaged during the trial. Participants should continue on the study but doses missed due to insufficient drug supply should be recorded as missed doses. Investigators can dispense the next due prescription early to cover for lost or damaged medication. According to local pharmacy policy, if surplus/ replacement medication is available (for example if another patient withdraws from treatment), this can be supplied as IMP for a study participant, provided the medication has not been dispensed from pharmacy, and the usual storage and packaging requirements are complied with.

Any study IMP which is dispensed and unused by the participant will be recalled and destroyed in the site pharmacy. For participants who withdraw during study treatment, they may be eligible to continue treatment on the NHS programme according to their usual clinician's judgement and local Trust guidelines.

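### A first negative HCV RNA after post-treatment week 16 is by implication a primary-endpoint failure, although Section 19.11 calls it a cure

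*Protocol*

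**What the plan says.** Section 19.11 sets out to reduce missing data on the primary outcome. Its rule is that "SVR12 will be defined as HCV RNA <15iu/mL from 12 to 16 weeks after end of treatment". Its reason for allowing a window is that "A negative HCV RNA at any point after 12 weeks post-treatment is clinically considered to be a sustained virological cure". It then adds: "Given data is time point specific, data outside of the defined window cannot be carried forward to replace missing data". On unsuccessful outcomes it says that "Non SVR12 will be differentiated by true viral relapse or missing data due to lost to follow up". The only negatives it classifies explicitly by timing are those before 12 weeks, which are non-SVR12.

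Sections 11.1, 11.3.1, 11.5 and 19.5 repeat the upper limit of 12 plus 4 weeks. The visit schedule in Section 13.8.2 allows the end-of-study visit up to 28 days late in both arms. Section 15.19 says: "Participants are considered lost to follow up if there is no end of study visit at post treatment week 12+4 weeks". Section 19.5 keeps every randomised participant who took study drug in the primary analysis and compares the arms by chi-square test.

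**The concern.** The clinical reason in Section 19.11 has no upper limit, but the rule built on it stops at week 16 and no reason is given for stopping there. A participant first sampled at, say, post-treatment week 18 with a negative result is cured by the protocol's own statement, yet has no route to being counted as SVR12. Filing that participant under missing data discards a known outcome.

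The endpoint is binary with 30 participants per arm, so a few such cases matter. Equal lateness lowers both response rates and costs power. Unequal lateness biases the contrast in either direction. The drug cost per SVR12 in Section 19.13 would carry the same misclassification.

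**Working it through.** **Classification.** Take a participant in the primary analysis set with no sample between weeks 12 and 16 and a negative sample at week 18.

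1. The 12 to 16 week definition (11.3.1, 19.5, 19.11) is not met.
2. Under 19.11, "data outside of the defined window cannot be carried forward to replace missing data". Even if this is read as aimed only at early results, step 1 already excludes the sample, and no section admits it.
3. There was no end-of-study visit by week 16, so 15.19 makes the participant lost to follow-up.
4. Section 19.11 lists missing data from loss to follow-up as a kind of non-SVR12.
5. Section 19.5 keeps the participant in the denominator.

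The result is a failure in the primary analysis.

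**The plan's own figure.** Section 19.1 gives 65% versus 95%, 80% power and 95% confidence (taken as two-sided 5%), with 24 per arm. The unpooled formula is n = (z₀.₉₇₅ + z₀.₈₀)² × [p₁(1−p₁) + p₂(1−p₂)] / (p₂−p₁)² = (1.960 + 0.842)² × (0.2275 + 0.0475) / 0.30² = 23.98, so 24. The stated figure reproduces.

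**Power at the planned 30 per arm.** Sum the product of the two binomial probabilities over all outcome pairs for which the uncorrected chi-square test is significant at 5%. At 65% versus 95% this gives 88.0%.

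**Effect of late first samples.** Let f be the share of an arm first sampled after week 16, and assume these participants have their arm's cure rate. The counted rate is then p(1−f). The protocol gives no f, so the counts below are assumptions (1/30 = 3.3%, 2/30 = 6.7%, 3/30 = 10%).

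| Late participants | Counted rates, A vs B | Difference (points) | Exact power |
|---|---|---|---|
| None | 65.0% vs 95.0% | 30.0 | 88.0% |
| One per arm | 62.8% vs 91.8% | 29.0 | 80.0% |
| Two per arm | 60.7% vs 88.7% | 28.0 | 72.8% |
| Three per arm | 58.5% vs 85.5% | 27.0 | 66.1% |
| One, Arm B only | 65.0% vs 91.8% | 26.8 | 74.6% |
| Two, Arm B only | 65.0% vs 88.7% | 23.7 | 59.9% |
| One, Arm A only | 62.8% vs 95.0% | 32.2 | 91.2% |
| Two, Arm A only | 60.7% vs 95.0% | 34.3 | 93.7% |

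The Arm A rows are no gain. The extra power comes from a difference larger than the true 30 points.

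**Illustration on one hypothetical data set.** With 20/30 versus 28/30, the uncorrected chi-square gives p = 0.010. Recoding one Arm B cure as a failure (27/30) gives 0.028, and recoding two (26/30) gives 0.067. With continuity correction the three values are 0.024, 0.060 and 0.127.

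**The case against.** The strongest reply is that no sentence scores a negative after week 16 as non-SVR12. That is true: the scoring is an inference from several rules taken together. It still follows, because the definition alone excludes later results.

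A fixed window with missing counted as failure is also a legitimate prespecified convention, and a clinical rationale can sit beside a bounded endpoint. That stands too. What remains is that the stated rationale does not support the limit at week 16, and the limit works against the section's aim.

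A reader might infer that routine-care results from withdrawn participants are the most likely to be discarded. The documents do not support this. Sections 13.8.4, 13.9 and 13.10 tie those results to the nominal 3-month or 12-week point, although they state no upper limit. No visit is scheduled after the week-16 limit, so a late sample needs a delayed or unscheduled test.

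A reader might also infer a serious loss of power or a bias against Arm B. Section 19.2 expects few withdrawals, and Section 19.1 raises 24 to 30 per arm to cover losses. One late participant per arm still leaves the planned 80%. Nothing in the protocol says that lateness differs by arm or in which direction.

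Separating relapse from missing data in 19.11 means such a participant would not be reported as a relapse. The per-protocol analysis in 19.10 is optional and defined by adherence, so neither provision changes the primary result. A sensitivity analysis may sit in a statistical analysis plan that is not shown, so its absence is not claimed as a defect.

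Finally, simply opening the window until database lock would cause new problems. Withdrawn participants may take further HCV treatment outside the trial (13.9, 13.10). Arm A also reaches its endpoint at week 24 and Arm B at week 36 (11.6), so a common lock date would give Arm A about 12 more weeks to produce a late negative. Both objections stand and shape the fix.

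**Conclusion.** The concern holds as an internal inconsistency with a small, uncertain effect. The protocol's rules implicitly count a first negative after week 16 as a primary-endpoint failure, while Section 19.11 describes the same result as a cure.

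Each such participant moves an arm by 1/30 = 3.3 points. Every power figure below 88.0%, and the 93.7% for Arm A only, rests on assumed numbers of late participants, on late participants having their arm's cure rate, and on an uncorrected two-sided 5% chi-square test. The true number is probably small.

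The severity is minor to moderate. The documents do not support calling it a flaw that must be repaired before the trial can be interpreted.

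**What to change.** In Section 19.11, with matching edits to 11.1, 11.3.1, 11.5, 15.19 and 19.5:

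- Keep 12 to 16 weeks as the target visit.
- Where no in-window result exists, count a first HCV RNA below the limit as SVR12 if it was taken at or after 12 weeks from the end of trial-assigned treatment. Apply the same fixed maximum post-treatment time in both arms, not database lock, and require that no further HCV treatment was taken outside the trial.
- State how a late positive is classified (relapse or possible reinfection).
- Reserve the lost-to-follow-up label for participants with no eligible result.
- Report the strict 12 to 16 week analysis as a sensitivity analysis.

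At minimum, keep the strict window as primary and prespecify the analysis that counts late negatives as SVR as the sensitivity analysis.

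The cost is a late-result rule and slightly more analysis work. No visit is added, and Section 13.11 already keeps the trial open: "End of trial is defined as 3 months after the last randomised participant completes the study procedures". Settle the choice before outcomes are known, because in an open-label trial a later decision would be post hoc.
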